7.2 Adverse Event Monitoring

Adverse event data collection and reporting, which are required as part of every clinical trial, are done to ensure the safety of subjects enrolled in the studies as well as those who will enroll in future studies using similar agents. Adverse events are reported in a routine manner at scheduled times during a trial. Additionally, certain adverse events must be reported in an expedited manner to allow for optimal monitoring of subject safety and care.

All subjects experiencing an adverse event, regardless of its relationship to study drug, will be monitored until:

- the adverse event resolves or the symptoms or signs that constitute the adverse event return to baseline;
- > any abnormal laboratory values have returned to baseline;
- there is a satisfactory explanation other than the study drug for the changes observed; or
- death.

7.3 Definitions

7.3.1 Definition of Adverse Event

An adverse event (AE) is any untoward medical occurrence in a subject receiving study treatment and which does not necessarily have a causal relationship with this treatment. An AE can therefore be any unfavorable and unintended sign

(including an abnormal laboratory finding), symptom, or disease temporally associated with the use of an experimental intervention, whether or not related to the intervention.

7.3.2 Severity of Adverse Events

All non-hematologic adverse events will be graded according to the NCI Common Terminology Criteria for Adverse Events (CTCAE) version 4.0. The CTCAE v4 is available at http://ctep.cancer.gov/reporting/ctc.html

If no CTCAE grading is available, the severity of an AE is graded as follows:

Mild (grade 1): the event causes discomfort without disruption of normal daily activities.

Moderate (grade 2): the event causes discomfort that affects normal daily activities.

Severe (grade 3): the event makes the patient unable to perform normal daily activities or significantly affects his/her clinical status.

Life-threatening (grade 4): the subject was at risk of death at the time of the event.

Fatal (grade 5): the event caused death.

7.3.3 Serious Adverse Events

A "serious" adverse event is defined in regulatory terminology as any untoward medical occurrence that:

Results in death.

If death results from (progression of) the disease, the disease should be reported as event (SAE) itself.

Is life-threatening.

(the subject was at risk of death at the time of the event; it does not refer to an event that hypothetically might have caused death if it were more severe).

Requires in-patient hospitalization or prolongation of existing hospitalization for \geq 24 hours.

Results in persistent or significant disability or incapacity.

Is a congenital anomaly/birth defect

Is an important medical event

Any event that does not meet the above criteria, but that in the judgment of the investigator jeopardizes the subject, may be considered for reporting as a serious adverse event. The event may require medical or surgical intervention to prevent one of the outcomes listed in the definition of "Serious Adverse Event". For example: allergic bronchospasm requiring intensive treatment in an emergency room or at home; convulsions that may not result in hospitalization; development of drug abuse or drug dependency.

7.3.4 Unanticipated Problems:

The term "unanticipated problem" is found, but not defined in the regulations for the Protection of Human Subjects at 45 CFR 46, and the FDA regulations at 21 CFR 56. Guidance from the regulatory agencies considers unanticipated problems to include any incident, experience, or outcome that meets **each** of the following criteria:

- unexpected; and
- related or possibly related to participation in the research; and

• suggests that the research *places subjects or others at a greater risk of harm* (including physical, psychological, economic, or social harm) *than was previously known or recognized.*

Follow-up

All adverse events will be followed up according to good medical practices.

7.3.5 Reporting

Local events requiring expedited reporting, are submitted to the UTSW IRB through the UTSW eIRB and to the SCC DSMC Coordinator. Hardcopies or electronic versions of the eIRB report; the NCI ADEERS, FDA Form #3500A forms, or other sponsor forms, if applicable; and/or any other supporting documentation available should be forwarded to the DSMC Coordinator. The DSMC Coordinator forwards the information onto the DSMC Chairman who determines if immediate action is required. Follow-up eIRB reports, and all subsequent SAE documentation that is available are also submitted to the DSMC Chair who determines if further action is required.

The DSMC Chairperson reviews all serious adverse events within upon receipt from the DSMC Coordinator. The DSMC Chairperson determines whether action is required and either takes action immediately, convenes a special DSMC session (physical or electronic), or defers the action until a regularly scheduled DSMC meeting.

Telephone reports to: [name], PhD at [contact] or [name] at [contact]
UTSW SCC Data Safety Monitoring Committee Coordinator (if fax report is not available) within 1 working day to [contact].
Written reports to: [name], PhD, or [name] at [contact]
UTSW SCC Data Safety Monitoring Committee Coordinator Email: [contact] [contact] or deliver to NB 2.418
UTSW Institutional Review Board (IRB) Submit via eIRB with a copy of the final sponsor report as attached supporting documentation

1. Unexpected Adverse Events

Non-serious adverse events which are classified as both unexpected (in terms of nature, severity and frequency) and possibly related require reporting to the UTSW IRB within 10 working days of PI awareness.

2. SAEs

- i. Local unanticipated problems require expedited reporting, and are submitted to the UTSW IRB through the UTSW eIRB and to the SCC DSMC Coordinator. Hardcopies or electronic versions of the eIRB report; FDA Form #3500A forms, or other sponsor forms, if applicable; and/or any other supporting documentation available should be forwarded to the DSMC Coordinator. The DSMC Coordinator forwards the information onto the DSMC Chairman who determines if immediate action is required. Follow-up eIRB reports, and all subsequent SAE documentation that is available are also submitted to the DSMC Chair who determines if further action is required.
- ii. All local serious adverse events which occur on research subjects on protocols for which the SCC is the DSMC of record require reporting to the DSMC regardless of whether IRB reporting is required. Hardcopies or electronic versions of the FDA Form #3500A forms, or other sponsor forms, if applicable; and/or any other supporting documentation available should be forwarded to the DSMC Coordinator.
- iii. If the event occurs on a multi-institutional clinical trial coordinated by the Cancer Center, the DOT Manager or lead coordinator ensures that all participating sites are notified of the event and resulting action, according to FDA guidance for expedited reporting. DSMC Chairperson reviews all serious adverse events within upon receipt from the DSMC Coordinator. The DSMC Chairperson determines whether action is required and either takes action immediately, convenes a special DSMC session (physical or electronic), or defers the action until a regularly scheduled DSMC meeting.

Telephone reports to: [name], PhD at [contact] or [name] at [contact]
UTSW SCC Data Safety Monitoring Committee Coordinator (if fax report is not available) within 1 working day to [contact].
Written reports to:
Fax – [name], PhD or [name] at [contact].
UTSW SCC Data Safety Monitoring Committee Coordinator Email: [contact] [contact] or deliver to NB 2.418
UTSW Institutional Review Board (IRB) Submit via eIRB with a copy of the final sponsor report as attached supporting documentation

3. Unanticipated Problems

Unanticipated problems, including those that occur as non-local events, require reporting to the UTSW IRB within 10 working days of PI awareness of the event.

For further guidance for Investigators regarding safety reporting requirements for INDs and BA/BE studies, refer to FDA Draft Guidance document: http://www.fda.gov/downloads/Drugs/GuidanceComplianceRegulatoryInformation/GuidanceS/UCM227351.pdf

7.4 Steps to Determine If an Adverse Event Requires Expedited Reporting

Step 1: Identify the type of adverse event using the NCI Common Terminology Criteria for Adverse Events (CTCAE v4).

Step 2: Grade the adverse event using the NCI CTCAE v4.

Step 3:Determine whether the adverse event is related to the protocol therapy Attribution categories are as follows:

- Definite The AE *is clearly related* to the study treatment.
- Probable The AE *is likely related* to the study treatment.
 - Possible The AE *may be related* to the study treatment.
 - Unrelated The AE is clearly NOT related to the study treatment.

Note: This includes all events that occur within 30 days of the last dose of protocol treatment. Any event that occurs more than 30 days after the last dose of treatment and is attributed (possibly, probably, or definitely) to the agent(s) must also be reported accordingly.

Step 4: Determine the prior experience of the adverse event.

Expected events are those that have been previously identified as resulting from administration of the agent. An adverse event is considered unexpected, for expedited reporting purposes only, when either the type of event or the severity of the event is not listed in:

- the current known adverse events listed in the Agent Information Section of this protocol;
- the drug package insert;

_

• the current Investigator's Brochure

7.5 Reporting Requirements for Adverse Events

• The FDA should be notified within 7 business days of any unexpected fatal or life-threatening adverse event with possible relationship to study drug, and 15 business days of any event that is considered: 1) serious, 2) unexpected, and 3) at least possibly related to study participation.

INSERT PROPER REPORTING PROCEDURES REQUIRED BY SPONSOR

- Please email or fax the SAE Worksheet to:
- Astellas Pharma Global Development United States
- Email: [contact]
- [contact]
- Follow-up information for the event should be sent promptly (within 7 days) as necessary.
- Full details of the SAE should also be recorded on the medical records and on the CRF.
- The following minimum information is required:
- ISN/Study number
- Subject number, sex and age
- The date of report

- A description of the SAE (event, seriousness of the event)
- Causal relationship to the study drug
- The period for SAE reporting after the last intake of the study drug should be specified.
- Expedited Safety Reports: An unexpected adverse event is one for which the nature or severity is not consistent with the current Investigator's Brochure. The Sponsor will make this assessment for all reported serious adverse events. An adverse event which is serious, related, and unexpected may be termed a Suspected Unexpected Serious Adverse Reaction (SUSAR). The Investigator will ensure that all relevant information is provided as soon as possible to Astellas in order that the Sponsor may meet their obligations to report any SUSAR.

7.5.1 Routine Reporting

• All other adverse events- such as those that are expected, or are unlikely or definitely not related to the study participation- are to be reported annually as part of regular data submission.

7.6 Unblinding Procedures

This is an open-label study. Unblinding procedures will not be applicable.

7.7 Stopping Rules

Based on experience from a completed phase III study, enzatlutamide is generally well tolerated when given in combination with a GnRH agonist. The most prominent safety concerns are primarily related to the risk of seizures. No completed study has examined the combination of enzalutamide with a GnRH agonist and concurrent radiation. The general tolerability of this combination is anticipated to be similar to that of radiation with concurrent GnRH agonist therapy. However, the absence of unexpected adverse events must be verified and is the primary endpoint of this study. Adverse events will be measured by NCI CTCAE criteria and will be monitored and recorded for a period of 12 months from initiation of the combination of enzalutamide plus GnRH agonist. Enrollment in the trial will be halted if unacceptable levels of toxicity are found as defined by 3 or more patients withdrawing from the study due to AEs.

8.0 DRUG INFORMATION

8.1 Enzalutamide

- Other names for the drug: Xtandi, MDV3100
- Classification type of agent: oral androgen receptor inhibitor
- Mode of action: inhibits androgen-induced receptor activation (binding of androgens to ARs in the cytosol), inhibits nuclear translocation of activated ARs, and inhibits the association of the activated AR with chromatin
- Storage and stability: Enzalutamide capsules should be stored at 20 C to 25 C (68 F to 77 F) in a dry place. Excursions are permitted from 15 C to 30 C (59 F to 86 F).
- Protocol dose: Subjects will take four 40 mg capsules (160 mg) daily. Patients will be given one bottle of 120 capsules at every 4 week follow up visit.
- Route of administration for this study: oral

- Availability: provided by sponsor free of charge
- Side effects: Adverse events associated with enzalutamide that are most likely to occur in this study include asthenia/fatigue, back pain, diarrhea, arthralgia, hot flush, peripheral edema, musculoskeletal pain, headache, upper respiratory infection, muscular weakness, dizziness, insomnia, lower respiratory infection, hematuria, paresthesia, anxiety, and hypertension. Please refer to the Xtandi (enzalutamide) package insert for a comprehensive list of adverse events.
- Nursing implications:

8.2 GnRH agonist – For the purposes of this study we are only using Lupron. Additonal GnRH agonists are listed below for informational purposes only.

• Description: GnRH agonists are long-acting analogs of the native GnRH peptide and are effective at reducing serum testosterone. Analogs approved by the FDA.

- Supply: Commercially available.
- Storage: GnRH analogs should be stored as directed by the commercial supplier.

• Administration: GnRH analogs are administered with a variety of techniques, including subcutaneous insertion of a solid plug in the abdominal wall (Zoladex), intramuscular injection (Lupron), subcutaneous injection (Eligard), or insertion of a long-acting cylinder that slowly

Releases the agent (Viadur). The manufacturer's instructions should be followed. Toxicity: Consult the package insert for comprehensive toxicity information. Class-related toxicity is generally a manifestation of the mechanism of action and due to low testosterone levels. In the majority of patients testosterone levels increased above baseline during the first week, declining thereafter to baseline levels or below by the end of the second week of treatment. The most common side effect of GnRH analogs is vasomotor hot flashes; edema, gynecomastia, bone pain, thrombosis, and gastrointestinal disturbances have occurred. Potential exacerbations of signs and symptoms during the first few weeks of treatment is a concern in patients with vertebral metastases and/or urinary obstruction or hematuria which, if aggravated, may lead to neurological problems such as temporary weakness and/or paresthesia of the lower limbs or worsening of urinary symptoms. Other side effects include impotence and loss of libido, weight gain, depression, dizziness, loss of bone density, anemia, increased thirst and urination, unusual taste in the mouth, skin redness or hives, pain at injection site, and muscle mass and strength loss, hair changes, penile length and testicular volume loss, increased cholesterol, hypertension, diabetes exacerbation, emotional lability, nausea, vomiting, and rarely allergic generalized rash and difficulty breathing.

8.2.1 Return and Retention of Study Drug

Unused study drug (enzalutamide) will be documented and returned to the Simmons Comprehensive Cancer Center Pharmacy for destruction per Standard Operating Procedures

8.2.2 Subject compliance with the study agent, enzalutamide, will be monitored through use of a pill diary provided to each subject enrolled in the study. A new pill diary will be provided at every 4 week follow up visit for the duration of the administration of enzalutamide on the study.

9.0 CORRELATIVES/SPECIAL STUDIES

The goal of the planned laboratory correlative studies is to evaluate the proposed mechanism of action of enzalutamide plus GnRH agonist on patient tumor samples. The proposed mechanism of action of enzalutamide has been established in pre-clinical studies. However, to date the molecular mechanism of action has not been reported in primary prostate cancer tumors from

patients. The purpose of the proposed laboratory correlative studies is to examine androgen signaling inhibition by enzalutamide in primary tumor samples from patients. Submission of samples for correlative studies is mandatory for participation in this trial.

9.1 Sample Collection Guidelines

Up to 6 needle core biopsies will be collected using 18 gauge needles under TRUSguidance at each of two occasions as described in Section 4.4.2.2. Biopsies will be performed at study entry and following 8 weeks of treatment with combined enzalutamide plus GnRH agonist. Samples will be submitted to pathology laboratory for diagnosis and to UTSW tissue bank. Samples will be labeled with the subject's de-identified study number and collection date and delivered for analysis to:

[name], MD

Cleveland Clinic and also to [name] and [name] at UT Southwestern Medical Center.

9.2 Assay Methodology

9.2.1 Immunohistochemistry for Androgen receptor (AR) and Ki-67 will be done using routine immunohistochemical assay in a CLIA certified clinical laboratory at UTSW. The slides will be analysed under a light microscope to access cellular localization of the antibody. Tissue procured for diagnosis will be processed using routine tissue processing protocols followed for pathologic diagnosis.

9.2.2 Gene expression studies

Ligand-bound androgen receptor (AR) activity may be defined by the expression of androgen-responsive genes. *PSA*, *TMPRSS2* and *FKBP5* are among the most widely studied and validated among these genes.²⁴ RNA will be extracted from the collected prostate cancer tissue using the RNeasy system (Qiagen, Germantown, MD), and 1 µg RNA will be used in a reverse transcription reaction using the iScript cDNA Synthesis Kit (Bio-Rad, Hercules, CA). Quantitative-PCR (qPCR) analysis will be performed in triplicate using previously published primers for *PSA*, *TMPRSS2*, *FKBP5* and for the housekeeping gene *large ribosomal protein P0* (*RPLP0*).²⁵ Absolute qPCR SYBR Low Rox Mix (Fisher, Waltham, MA) will be used in 25 µl final reaction volume, in 96-well plates. The thermocycling reaction will carried out in an ABI 7500 Real Time PCR machine (Applied Biosystems, Foster City, CA). Accurate quantitation of each mRNA will be achieved by normalizing the sample values to *RPLP0* and to vehicle treated cells. Samples will be labeled with the subject's de-identified study number and collection date and delivered for gene expression analysis to

[name]. Kendrick Family Endowed Chair for Prostate Cancer Research Cleveland Clinic Lerner Research Institute Cancer Biology, NB40 [name]

9.2.3 Genomic sequence analysis of selected steroidogenic enzymes

The first and rate-limiting step for metabolic flux from adrenal dehydroepiandrosterone (DHEA) to dihydrotestosterone (DHT) is catalyzed by 3β-hydroxysteroid dehydrogenase/isomerase, which is encoded by two isoenzymes, *HSD3B1* and *HSD3B2*.²⁶ Our unpublished observations suggest that genomic alterations of one or both of these genes may contribute to the development of resistance to various hormonal therapies in prostate cancer. Genomic DNA will be prepared from collected samples (tumor and matched peripheral blood) using DNeasy Blood and Tissue Kit (QIAGEN,

Germantown, MD). PCR products of the promoter region, all exons, exon-intron junctions and the 3'-UTR will be sequenced to identify mutations in *HSD3B1* and *HSD3B2*. The primers and annealing temperature were described previously.²⁷ To sequence the 3' flanking region of *HSD3B1*, primer set (Forward: 5'-ATGTGGAGGGAGGTGTGAGT-3' and Reverse: 5'-ACGGAGATGGGTCTCTTCCA-3') will be used with an annealing temperature of 62°C. Genotyping PCR reaction (50 µl) consisted of 30-100 ng genomic DNA, 1 x PCR buffer with 0.2 mM dNTP, 0.2 µM of each primer, and 0.5 µl Phusion High-Fidelity DNA Polymerase (New England BioLabs Inc, Ipswich, MA). Tumor and germline sequences will be compared in each individual patient to assess for somatically acquired mutations. Samples will be labeled with the subject's de-identified study number and collection date and delivered for genomic sequence analysis to

[name]. Kendrick Family Endowed Chair for Prostate Cancer Research Cleveland Clinic Lerner Research Institute Cancer Biology, NB40 [name]

9.3 Specimen Banking

The tissue used for diagnosis will be stored for 10 years in the CLIA certified clinical Pathology laboratory at UTSW. The tissue procured for research will be stored snap frozen in the UTSW tissue bank indefinitely or until used up. Serum and tissue may be used for future additional studies with specific consent from study subjects. If future use is denied or withdrawn by the subject, best efforts will be made to stop any additional studies and to destroy the specimens.

The specimens, DNA, and their derivatives may have significant therapeutic or commercial value. The Informed Consent form contains this information and informs the subject that there is the potential for financial gain by UT Southwestern, the investigator, and the study sponsors Medivation, Inc. and Astellas Pharma US, Inc.

The following information obtained from the subject's medical record may be provided to research collaborators when specimens are made available:

- Diagnosis
- Collection time in relation to study treatment
- Clinical outcome if available
- Demographic data

10.0 STATISTICAL CONSIDERATIONS

10.1 Study Design/Study Endpoints

This is an open-label, single-arm, single-center prospective pilot study of enzalutamide plus GnRH agonist treatment combined with EBRT in the treatment of men with high-risk localized or locally advanced prostate cancer. Select patients with regional lymph node involvement (N1 disease) are also eligible to participate in this study.

Primary endpoint: to determine the safety and tolerability of combining enzlutamide plus a GnRH agonist with EBRT up to 12 months following initiation of treatment with enzalutamide plus GnRH agonist.

Secondary endpoints:

1. Molecular markers of androgen signaling and cell death in prostate biopsy samples

- a. Inhibition of androgen-regulated gene expression (potential targets to include NDRG1, FKBP5, TMPRSS2, and PSA) by qRT-PCR
- b. Inhibition of androgen receptor (AR) nuclear localization and enhancement of apoptotic cell death measured by immunohistochemistry (IHC)
- c. Androgen metabolism in prostate biopsy samples
- 2. Serum PSA, testosterone, dehydroepiandrosterone (DHEA), and DHEA-sulfate (DHEA-S) following combination therapy with enzalutamide plus GnRH agonist therapy prior to initiation of radiation therapy
- 3. Changes in prostate tumor volume and activity following 2 months of combined enzalutamide plus GnRH therapy compared to baseline as measured by multiparametric magnetic resonance imaging (MRI)

The trial will be halted if unacceptable levels of toxicity are found as defined by 3 or more patients withdrawing from the study due to AEs or if 3 or more patients experience SAEs.

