A formal interim analysis of overall survival was performed at 520 events (80% of the 650 targeted number of events for final analysis) and demonstrated a statistically-significant increase in the duration of survival among patients treated with MDV3100 compared with patients treated with placebo (hazard ratio = 0.631 [95% Cl: 0.529, 0.752], p < 0.0001). Median survival was 18.4 months in the MDV3100 arm and 13.6 months in the placebo arm (Δ = 4.8 months). The survival benefit was seen in all pre-specified patient subgroups defined by age, geographic region, Eastern Cooperative Oncology Group (ECOG) performance status, pain score, Gleason score, number of prior chemotherapy regimens, type of disease progression at study entry, baseline level of PSA, baseline level of hemoglobin, and baseline level of lactate dehydrogenase (LDH). There were also statistically-significant increases in time to PSA progression; radiographic progressionfree survival (assessed by computed tomography ICT) or magnetic resonance imaging [MRI] and by bone scan); time to first skeletal-related event; PSA response, and overall objective soft tissue radiographic response among patients treated with MDV3100 compared to placebo. In addition, statistically-significant differences favoring MDV3100 over placebo in pain palliation and pain progression rate at Week 13 were also observed.11

Of the MDV3100-treated patients, 98.1% reported at least 1 treatment-emergent adverse event as compared to 97.7% of placebo patients as of the data cutoff date of 25 September 2011. Serious adverse events were reported in 33.5% of MDV3100-treated patients as compared with 38.6% of placebo-treated patients. Of the MDV3100-treated patients, 7.6% discontinued study drug due to adverse events as compared with 9.8% of placebo patients.

Adverse events reported by those treated with MDV3100 with an incidence at least 2% greater than that among those who received placebo included fatigue, diarrhea, hot flush, musculoskeletal pain, headache, insomnia, anxiety, hypertension, nasopharyngitis, pollakiuria, fall, pruritus, dry skin, and musculoskeletal stiffness. Serious adverse events reported with an incidence of at least 0.5% and more frequently by MDV3100-treated patients compared to placebo patients were spinal cord compression, general physical health deterioration, hematuria, pneumonia, bone pain, metastatic pain, pathologic

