5.2 Procedures During Treatment

Subjects will receive treatment in the following phases:

- Neo-adjuvant: Subjects will receive treatment with enzalutamide plus GnRH agonist for 8-10 weeks prior to the initiation of EBRT
- Concurrent: Subjects will continue to receive treatment with enzalutamide plus GnRH agonist for the duration of EBRT (8-10 weeks)
- Adjuvant: Subjects will receive treatment with enzalutamide plus GnRH agonist following completion of EBRT until a total duration of 24 weeks of enzalutamide plus GnRH agonist treatment has been completed
- Maintenance: Subjects will continue to receive GnRH agonist therapy following completion of treatment with enzalutamide to achieve a total of 24 - 36 months of GnRH agonist treatment.
- During the neo-adjuvant, concurrent, and adjuvant phases, subjects will receive treatment with enzalutamide plus GnRH agonist therapy for six 28 day cycles for a total duration of 24 weeks.

5.2.1 Prior to Each Treatment Cycle During Neo-Adjuvant, Concurrent, and Adjuvant phases (weeks 1-24):

- Physical exam, vital signs
- Hematology
- Serum chemistries
- Toxicity evaluation

5.2.2 Day – 56 to – 14:

- Procedure:
- o MRI pelvis
- TRUS-guided prostate biopsies

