11.3 Data Management and Monitoring

The UTSW Simmons Cancer Center (SCC) Data Safety Monitoring Committee (DSMC) is responsible for monitoring data quality and patient safety for all UTSW SCC clinical trials. As part of that responsibility, the DSMC reviews all local serious adverse events in real time as they are reported and reviews adverse events on a quarterly basis. The quality assurance activity for the Clinical Research Office provides for periodic auditing of clinical research documents to ensure data integrity and regulatory compliance.

The SCC DSMC meets quarterly and conducts annual comprehensive reviews of ongoing clinical trials, for which it serves as the DSMC of record.

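### Sections 7.7 and 10.1 give different safety stopping rules, and the section headed Stopping Rules omits the SAE trigger

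*Combined protocol and SAP*

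**What the plan says.** Section 7.7, headed Stopping Rules, ends: "Enrollment in the trial will be halted if unacceptable levels of toxicity are found as defined by 3 or more patients withdrawing" from the study because of AEs. It names no SAE criterion, and the action is on enrollment.

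Section 10.1 ends with a rule whose action is on the trial as a whole. Its triggers are "3 or more patients withdrawing from the study due to AEs or if 3 or more patients experience SAEs".

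Neither section refers to the other, and no other section says which takes precedence. Both are current operative text.

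Three other provisions bear on the point:

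- **SAE definition (section 7.3.3).** One criterion is "Requires in-patient hospitalization or prolongation of existing hospitalization for" 24 hours or more. The definition carries no attribution limit.
- **Dose modification (section 4.2, Table 4.2.2).** For non-hematological toxicity, enzalutamide is held at the first grade 3-4 episode, held and then reduced to 80 mg at the second, and the subject is removed only at the third.
- **SAE oversight.** Under section 7.3.5, local SAEs "require reporting to the DSMC regardless of whether IRB reporting is required". Section 11.3 adds that "the DSMC reviews all local serious adverse events in real time as they are reported".

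**The concern.** Safety and tolerability are the primary endpoint, and section 7.7 itself notes that no completed study has tested this combination with concurrent radiation. These sentences are the only numeric trial-level safety limit in the protocol, so they should read one way.

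The versions differ in two respects. On the trigger, 7.7 has one limb and 10.1 has two. On the action, 7.7 stops new entries while 10.1 stops the trial. Someone who consults only the section named for stopping rules would miss both the SAE limb and the wider action. The third patient with an SAE could then pass without the halt that 10.1 requires.

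**Working it through.** **1. Can the rules give different answers on the same data?** Yes. A patient hospitalized for a day with a first grade 3 event has an SAE under 7.3.3, but under Table 4.2.2 has enzalutamide held and stays on study. Three such patients meet 10.1 and not 7.7. The reverse cannot happen, because three AE withdrawals meet both. The rules are therefore nested.

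**2. How likely is the gap?** The plan gives no operating characteristics for either rule, so there is no figure to reproduce. Inputs:

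- Sample size: 7 (Study Summary) or 10 (section 10.2), so both are shown.
- SAE rate: not given for this population. I assume 5%, 10% and 20%, and add the phase III figures in section 1.2.2: "Serious adverse events were reported in 33.5% of MDV3100-treated patients as compared with 38.6% of placebo-treated patients". That trial enrolled much sicker patients.
- AE withdrawal rate: 7.6%, a proxy from the same trial, in which "7.6% discontinued study drug due to adverse events". Stopping the drug is not the same as leaving the study.

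With S the number of patients with an SAE, W the number of AE withdrawals, and p the event rate:

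P(X ≥ 3) = 1 − (1−p)^n − n·p·(1−p)^(n−1) − [n(n−1)/2]·p²·(1−p)^(n−2)

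Example, n = 7 and p = 0.10: 1 − 0.4783 − 0.3720 − 0.1240 = 0.0257.

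For W at p = 0.076: P(W ≥ 3) = 0.0122 (n = 7) and 0.0351 (n = 10).

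The chance that 10.1 is met on SAEs while 7.7 is not lies, whatever the overlap between SAEs and withdrawals, within

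P(S ≥ 3) − P(W ≥ 3) ≤ P(S ≥ 3 and W < 3) ≤ P(S ≥ 3), with the lower limit set to 0 if negative.

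| SAE rate | n=7: P(S≥3) | n=7: 10.1 met, 7.7 not | n=10: P(S≥3) | n=10: 10.1 met, 7.7 not |
|---|---|---|---|---|
| 5% (assumed) | 0.4% | 0 to 0.4% | 1.2% | 0 to 1.2% |
| 10% (assumed) | 2.6% | 1.4% to 2.6% | 7.0% | 3.5% to 7.0% |
| 20% (assumed) | 14.8% | 13.6% to 14.8% | 32.2% | 28.7% to 32.2% |
| 33.5% (phase III drug arm) | 43.3% | 42.1% to 43.3% | 70.5% | 67.0% to 70.5% |

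At the 38.6% placebo-arm rate, P(S ≥ 3) is 54.9% (n = 7) and 80.9% (n = 10).

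**3. How much treatment falls where halting enrollment does nothing?** Section 10.2 expects seven subjects in about four months (17.4 weeks). Section 5.2 gives enzalutamide "for six 28 day cycles for a total duration of 24 weeks". Assume even entry with six gaps of 17.4/6 = 2.9 weeks. Drug-weeks before the last entry are the sum over patients of min(24, last entry − own entry).

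- n = 7, last entry at week 17.4: 17.4 + 14.5 + 11.6 + 8.7 + 5.8 + 2.9 + 0 = 60.9 of 7 × 24 = 168. After the last entry: 107.1, or 63.75%.
- n = 10, last entry at week 26.1: 24 + 23.2 + 20.3 + 17.4 + 14.5 + 11.6 + 8.7 + 5.8 + 2.9 + 0 = 128.4 of 240. After: 111.6, or 46.5%.
- With spacing 17.4/7 = 2.49 weeks instead: 115.8 of 168 (68.9%) and 128.1 of 240 (53.4%).

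**The case against.** The strongest reply is that there is no true conflict. Section 10.1 contains all of the 7.7 trigger, 7.7 does not say that withdrawals are the only trigger, and section 11.4 requires the protocol to be followed as written. A team that reads the whole document already halts on three SAE patients. This is also a single-center study of 7 to 10 patients, and under section 7.3.5 the DSMC chair reviews every SAE on receipt and can act at once. This stands as a limit on harm. It does not make the text consistent: the DSMC provisions give discretion, not a numeric halt at the third SAE patient, and nothing directs a reader of 7.7 to 10.1.

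Second, the large probabilities come from docetaxel-treated castration-resistant disease, whereas this trial excludes bone and visceral metastases. That is right. The 33.5% and 38.6% rows are poor guides, the 5% to 20% range is assumed, and at 5% the SAE limb is less likely to fire than the withdrawal limb.

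Third, some events count under both rules. Any seizure removes the subject (section 4.2), and convulsions are a listed SAE example. The bounds above hold whatever the overlap.

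Fourth, the protocol does not define what halting the trial means for patients already on drug. That also stands: the share of drug-weeks shows where halting enrollment has no effect, not how much exposure 10.1 would prevent.

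**Conclusion.** The inconsistency is real in both trigger and action, and the section named for stopping rules carries the narrower version. If the SAE rate is 10% to 20%, the chance of meeting 10.1 on SAEs without meeting 7.7 is about 1.4% to 14.8% with 7 patients and 3.5% to 32.2% with 10. At 5% it is negligible to about 1%. These figures assume independent patients with a common event rate, a fully enrolled cohort, and 7.6% as a stand-in for AE withdrawal.

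This should be fixed, but it is not a major flaw. Following 10.1 satisfies both sections, the DSMC sees the SAEs in any case, and no test or estimate depends on the rule.

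**What to change.** Replace the last sentence of 7.7 with the last sentence of 10.1, so that both sections halt the trial on "3 or more patients withdrawing from the study due to AEs or if 3 or more patients experience SAEs". This uses a threshold already in the protocol and adds no patients or procedures.

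The price depends on which section is now taken to govern. If it is 10.1, nothing changes. If it is 7.7, a pause becomes more likely, by the margins in the table. Because the SAE limb counts events of any cause, background events alone could trigger it.

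While making the edit, the sponsor should decide three things that the current sentence leaves open: what halting means for patients on treatment, what counts as a withdrawal, and whether the SAE limb should be limited by attribution.
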